8.3. Time Period and Frequency for Adverse Event Assessment and Follow-up

8.3.1. Adverse Event and Serious Adverse Event Monitoring

All AEs regardless of seriousness, severity, or causality will be collected from the time the patient/parent(s)/legal guardian(s) provides written informed consent/assent through 30 days (+3 days) after final dose of study drug (Safety Follow-up TCs, Section 7.5).

For patients who receive study drug in the Double-Blind Phase and do not enter the OLE Phase of the study, if an Investigator becomes aware of an SAE that occurs at any time after the patient's study participation and the Investigator considers the event to be possibly related to the study drug, the Investigator should report the SAE to the Sponsor as described in Section 8.4.1.

8.3.2. Follow-up of Events

After the occurrence of an AE or SAE, the Investigator is required to follow each patient proactively and provide further information on the patient's condition. All AEs and SAEs documented at a previous visit or contact and designated as ongoing will be reviewed at subsequent visits or contacts.

All AEs and SAEs will be followed after the last scheduled study visit until the event resolves, the condition stabilizes, or the event is otherwise explained or judged by the Investigator to be no

longer clinically significant (unless the patient is lost to follow-up or the patient/parent(s)/legal guardian(s) withdraws consent).

The Investigator will assess the outcome of each AE using the following categories:

- Recovered/Resolved: The event resolved, or the patient recovered without sequelae. An event (either serious or nonserious) occurred and had an endpoint, and the patient experienced no restrictions. Examples include stent placement for coronary artery disease (a device implanted is not a sequela), an appendectomy (a scar is not a sequela), a postoperative wound infection, or an upper respiratory tract infection.
- Recovered/Resolved with sequelae: The event has at least one secondary outcome that may result in permanent disability, functional limitation, or both. Examples include hip replacement resulting in foot drop (foot drop is not the intended outcome but is a risk of surgery), stroke resulting in paralysis, or emboli formation after a bacterial infection resulting in a renal infarct and loss of renal function.
- **Recovering/Resolving:** The event is improving.
- Not recovered/Not resolved: At the end of the study, an event either has not changed in intensity or may not have recovered to baseline values, and the outcome is unknown. Examples include headache, low-grade fever, or nausea.
- Unknown: The patient is lost to follow-up, and the status of the event is unknown.
- Death

8.4. Reporting Procedures

8.4.1. Reporting Serious Adverse Events to the Sponsor

During this study, if the Investigator determines that an event meets the protocol definition of an SAE, regardless of relationship to study drug, they must notify the Sponsor as soon as possible but no later than **24 hours of becoming aware of the SAE**. The SAE report form (completed with all available information) must be sent to the Sponsor via e-mail or facsimile as soon as possible but no later than **within 24 hours of the Investigator becoming aware of the SAE**. The investigator must be diligent about providing additional information as needed. The Investigator must also enter the SAE information into the eCRF as soon as possible thereafter.

In the initial email, the Investigator must provide to the Sponsor the following eCRF pages, completed to the greatest extent possible:

- AE record
- Medical history
- Prior and concomitant medications

Also, any laboratory test results, diagnostic test results, or medical reports relevant to the SAE should be provided; however, certain patient identifying information (i.e., name, address, and other identifying information not collected in the patient's eCRF) is to be redacted from copies of the patient's medical records.

In rare circumstances and in the absence of email capacity, a copy of the SAE reporting form can be sent to the Sponsor by overnight mail. Initial notification of the event via telephone or email does not replace the need for the Investigator to complete the appropriate SAE form within the time frames outlined and email the form (or in the absence of email/scanning capacity--overnight mail is acceptable in rare cases). In addition, the AE/SAE information for the event needs to be entered in the eCRF.

If the Investigator does not have all information regarding an SAE, he/she must not wait to receive additional information before notifying the Sponsor of the event. The SAE must be updated when additional information is received. Follow-up information received on all SAEs must be forwarded to the Sponsor using the same 24-hour timelines as for an initial report.

In the event of a medical emergency in which knowledge of the patient's treatment assignment may influence their clinical care, the Investigator has the option to unblind the patient's treatment assignment via the IRT system. The Investigator should make every effort to contact the Medical Monitor prior to unblinding unless this would adversely delay appropriate medical care. The Medical Monitor will not be unblinded and will only provide assistance to the Investigator. The reasons for unblinding must be noted in the source documents. The Investigator must not disclose the patient's treatment assignment to anyone who does not need the information based on their direct involvement in the patient's clinical care. Disposition of patients who are unblinded due to a medical emergency will be determined following discussion with the Sponsor.

In the event of death, every effort should be made to obtain a death certificate and if possible, an autopsy report. Death is considered an outcome of an event; however, if the event that resulted in death is unknown, death will be recorded as the event.

8.4.2. Reporting Unanticipated Problems to the Sponsor

If the Investigator determines that an event meets the protocol definition of an unanticipated problem, he/she must notify the Sponsor within 24 hours of becoming aware of the problem.

The following information should be included with unanticipated problem reporting:

- Protocol identifying information: protocol title, protocol number, and Investigator's name
- A detailed description of the event, incident, experience, or outcome
- An explanation of the basis for determining that the event, incident, experience, or outcome represents an unanticipated problem

It is the Investigator's responsibility to report unanticipated problems to the Sponsor and the IRB, as required by local regulations.

8.4.3. Regulatory Reporting Requirements

The Investigator must promptly report all SAEs to the Sponsor in accordance with the procedures detailed in Section 8.4.1. The Sponsor has a legal responsibility to notify, as appropriate, both the local regulatory authority and other regulatory agencies about the safety of a product under clinical investigation. Prompt notification of SAEs by the Investigator to the appropriate project contact for SAE receipt is essential so that serious suspected adverse

reactions that are either unexpected or observed with increasing occurrence can be reported and legal obligations and ethical responsibilities regarding the safety of other patients are met.

Investigator letters are prepared according to Sponsor policy and are forwarded to Investigators as necessary. An Investigator letter is prepared for any suspected adverse reaction that is both serious and unexpected. The purpose of an Investigator letter is to fulfill specific regulatory and cGCP requirements regarding the product under investigation.

The Investigator, or responsible person according to local requirements, must comply with requirements related to the reporting of SAEs to the IRB.

The Sponsor is responsible for informing IRBs, Investigators, and regulatory authorities of any finding that could adversely affect the safety of patients or affect the conduct of the study. Events will be reported to regulatory authorities in accordance with expedited reporting requirements.

8.4.4. Pregnancy Reporting

Pregnancy is not considered an SAE; however, it is documented and followed in the same manner as an SAE. Any patient who becomes pregnant during the study must be withdrawn from the study immediately. Patients who become pregnant within 30 days after receiving their final dose of study drug should also notify the Investigator. The Investigator must attempt to follow the pregnancy to term or termination in order to report on the outcome and health status of the mother and child.

The Investigator must notify the Sponsor of any pregnancy by completing a Pregnancy Form and emailing it to the Sponsor within 24 hours of becoming aware of the pregnancy.

9. STATISTICAL CONSIDERATIONS

9.1. General Considerations

All safety and efficacy data will be listed and summarized. Unless otherwise specified, Baseline is defined as the last observed measurement, whether scheduled or unscheduled, prior to study drug administration. Safety and efficacy endpoints will be summarized by treatment group and the active treatment groups pooled. Continuous variables will be summarized using the number of patients with data (n), mean, standard deviation (SD), median, minimum, and maximum. Selected continuous variable summaries will also include the standard error. Categorical variables will be summarized using frequency counts and percentages.

The statistical analysis plan (SAP) will provide further details for statistical methodology. If the statistical analyses described in the final SAP and final protocol differ, the statistical analyses in the SAP will be used for the analyses presented in the clinical study report (CSR). Substantive changes from the analyses specified in the protocol will be described in the SAP and in the CSR.

In general, continuous variables will be summarized using the number of non-missing values, mean, SD, median, minimum, and maximum; categorical variables will be summarized using the count and the percentage of patients in each category. All values summarized will also be presented in listings.

All analyses will be performed using SAS® version 9.4 or higher, unless otherwise specified.

9.1.1. Estimand

The primary efficacy endpoint is defined as the change in mean ESS-CHAD (parent/caregiver version) score from Baseline to Week 11 for higher dose pitolisant compared with placebo.

The target population is all patients in the intent-to-treat (ITT) population with PWS as defined by the inclusion/exclusion criteria.

A treatment policy strategy will be used to address intercurrent events. No special data handling will be used for patients who initiate concomitant medications, have intermittent missing data, or discontinue study medication (even if they report data following discontinuation of study medication). No explicit imputation of missing data will be performed; the mixed model repeated measures (MMRM) approach assumes data are missing at random and will provide unbiased results if this is the case. Sensitivity analyses will explore the results under different analysis assumptions.

9.1.2. Multiple Comparisons

The study objective is to evaluate the effectiveness of pitolisant in treating EDS for the purposes of informing the design of future studies. As such, the relative strengths of all measures are of interest and p-values will be reported with no formal multiplicity adjustments.

The following order reflects the endpoints of most interest and greater consideration will be given to successful endpoints higher in the list, particularly when all preceding endpoints have a significant p-value.

• Primary endpoint: Change in ESS-CHAD (parent/caregiver version) score from Baseline to Week 11 for the higher dose pitolisant group compared with placebo.

- Primary endpoint: Change in mean ESS-CHAD (parent/caregiver version) score from Baseline to Week 11 for the lower dose pitolisant group compared with placebo.
- Primary endpoint: Change in mean ESS-CHAD (parent/caregiver version) score from Baseline to Week 11 for the combined pitolisant dose groups compared with placebo.
- Secondary endpoint: Change in CaGI-S for EDS from Baseline to Week 11 for the higher dose pitolisant group compared with placebo.
- Secondary endpoint: Change in CGI-S for overall clinical status from Baseline to Week 11 for the higher dose pitolisant group compared with placebo.
- Secondary endpoint: Change in CaGI-S for EDS from Baseline to Week 11 for the lower dose pitolisant group compared with placebo.
- Secondary endpoint: Change in CGI-S for overall clinical status from Baseline to Week 11 for the lower dose pitolisant group compared with placebo.

Likewise, the effect of treatment with pitolisant (higher dose, lower dose, and pooled) compared with placebo on other secondary outcomes will be tested in the order outlined in the SAP. These include the change from Baseline to Week 11 in behavior as measured by ABC-C and MERS-R-PWS; cognition as measured by Cogstate Detection, Identification and One Back tests; and perceived caregiver burden as measured by ZBI-22.

9.1.3. Missing Data

Every effort will be made to retain patients in the study; however, patients are able to withdraw from the study at any time for any reason. Patients who withdraw early will be asked to return to the clinic for an ET visit for completion of assessments (Section 7.3.3 and Section 7.4.3). No explicit imputation will be performed for the primary analysis; however, the MMRM model will yield unbiased results under the assumption that data are missing at random (MAR).

A sensitivity analysis will be performed using a hypothetical strategy. In this approach, the unobserved data following discontinuation for lack of efficacy (LOE) or AEs will be assumed to follow the placebo distribution at the matching visit, conditioned on the patient's observed data (including baseline). Patients who discontinue for all other reasons and intermittent missing data will be assumed to be MAR.

This will be implemented using a three-stage multiple imputation (MI) approach:

- 1. Intermittent missing data will be imputed within treatment group using MI under a MAR assumption with covariates for site and observed values at all available time points (including baseline). Twenty values will be produced using the Markov Chain Monte Carlo (MCMC) method implemented with the SAS MI procedure, producing a monotone missing data pattern.
- 2. Patients who drop out for reasons other than LOE or AEs will likewise have their missing values following dropout imputed within treatment group with covariates for site and observed values at all available time points (including baseline).
- 3. Finally, patients who withdraw from the study due to LOE or AEs will have their missing values following discontinuation imputed using the placebo group distribution, regardless of their assigned treatment group.

9.2. Determination of Sample Size

The sample size is 60 patients (20 in the lower dose pitolisant group, 20 in the higher dose pitolisant group, and 20 in the placebo group). Prior research suggests that the ESS-CHAD SD falls between 5 to 6; at the lower end of this range, the study would be powered at 80% to detect a difference of 3.9 between the pooled pitolisant groups and placebo group. However, as a proof of concept, statistical separation is not a strict objective of the trial. The proposed sample size will yield a 95% confidence interval of ± 2.7 with an SD of 5 and ± 3.2 with an SD of 6; this will give sufficient precision to inform future studies.

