Open-Label Extension Phase

Long-term effectiveness of pitolisant as measured by ESS-CHAD (parent/caregiver version), CaGI-S for EDS, CGI-S for overall clinical status related to PWS, ABC-C, MERS-R-PWS, Cogstate Detection Test, Cogstate Identification Test, Cogstate One Back Test, ZBI-22, and HQ-CT in conjunction with the FSZQ will be assessed during the first year of participation (through Visit 9) in the OLE Phase of the study. After the first year, only ESS-CHAD (parent/caregiver version), CaGI-S, and CGI-S will continue to be assessed.

PHARMACOKINETIC AND PHARMACODYNAMIC ENDPOINTS

- C_{max} of pitolisant and its major metabolite, BP1.3484
- AUC_{last} after administration of pitolisant
- t_{max} of pitolisant
- Exposure-response relationship between pitolisant levels and change in efficacy measures

SAFETY ENDPOINTS

Safety will be assessed by monitoring the incidence of AEs and changes in clinical laboratory test results, vital signs, and 12-lead ECG results, along with additional safety assessments (suicidality, anxiety, and monitoring of seizures in patients with seizure disorder) from Baseline to Week 11 in the Double-Blind Treatment Phase and from Baseline to study completion in the OLE Phase.

STATISTICAL METHODS: All analyses will be performed using SAS[®] version 9.4 or higher, unless otherwise specified.

Primary Efficacy Analyses: Summary statistics (mean, standard deviation, median, minimum, maximum) for the primary efficacy endpoint of change in mean ESS-CHAD (parent/caregiver version) score from Baseline to Week 11 for pitolisant compared with placebo will be reported by treatment group and for the active groups combined. The change from Baseline will be analyzed in a mixed model repeated measures (MMRM) analysis. Fixed effects will be included for treatment, visit, treatment*visit interaction, Baseline value, and site. An unstructured covariance matrix will be utilized and if this fails to converge, then first-order autoregressive and compound symmetry will be attempted in that order; Kenward-Rogers degrees of freedom will be used. Least square (LS) means, standard errors, and the LS mean differences (each treatment vs placebo and the pooled active groups vs placebo) will be reported. All estimates will be generated from a single model, i.e., the pooled estimates will be created via model contrasts. The primary contrast of interest is the difference in the higher dose group versus placebo at Week 11.

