Secondary Efficacy Analyses: Continuous outcomes collected at multiple time points will be analyzed with summary statistics (mean, standard deviation, median, minimum, maximum) for the absolute values and change from baseline at each timepoint by treatment group and for the active groups combined. The change from Baseline will be analyzed using an MMRM approach. Fixed effects will be included for treatment, visit, treatment×visit interaction, and baseline value. An unstructured covariance matrix will be utilized and if this fails to converge, then first-order autoregressive and compound symmetry will be attempted in that

order; Kenward-Rogers degrees of freedom will be used. Least square means, standard errors, and the LS mean differences (each treatment vs placebo and the pooled active groups vs placebo) at each time point will be reported. All estimates will be generated from a single model, i.e., the pooled estimates will be created via model contrasts. The primary contrast of interest is the difference in the higher dose group versus placebo at Week 11.

OLE Efficacy Analyses: Results in the OLE Phase will be tabulated with summary statistics for continuous outcomes and frequencies and percentages for categorical outcomes. No p-values will be reported for the OLE Phase. Baseline for the OLE will be the pre-double-blind-treatment baseline (identical to that used for the double-blind analyses). Details of open-label analyses will be fully described in the statistical analysis plan (SAP).

Safety Analyses: All safety data will be listed and summarized for the Double-Blind Treatment Phase and OLE separately in a similar tabulation format as for efficacy. No formal statistics will be performed for the safety analysis.

Determination of Sample Size: The sample size is 60 patients (20 in the lower dose pitolisant group, 20 in the higher dose pitolisant group, and 20 in the placebo group). Prior research suggests that the ESS-CHAD (parent/caregiver version) SD falls between 5 to 6; at the lower end of this range, the study would be powered at 80% to detect a difference of 3.9 between the pooled pitolisant groups and placebo group. However, as a proof of concept study, statistical separation is not a strict objective of the trial. The proposed sample size will yield a 95% confidence interval of ± 2.7 with an SD of 5 and ± 3.2 with an SD of 6; this will give sufficient precision to inform future studies.

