9.4.2. Efficacy Analysis

9.4.2.1. Double-Blind Treatment Phase

9.4.2.1.1. Primary Efficacy Analysis

Summary statistics (mean, SD, median, minimum, maximum) for the primary efficacy endpoint of change in mean ESS-CHAD (parent/caregiver version) score from Baseline to Week 11 for pitolisant compared with placebo will be reported by treatment group and for the active groups combined. The change from Baseline will be analyzed in an MMRM analysis. Fixed effects will be included for treatment, Baseline value, visit, and treatment×visit interaction. An unstructured covariance matrix will be utilized, and if this fails to converge, then first-order autoregressive and compound symmetry will be attempted in that order; Kenward-Rogers degrees of freedom will be used. Least square (LS) means, standard errors, and the LS mean differences (each treatment vs placebo and the pooled active groups vs placebo) will be reported. All estimates will be generated from a single model, i.e., the pooled estimates will be created via model contrasts. The primary contrast of interest is the difference in the higher dose group versus placebo at Week 11.

Sensitivity analyses will utilize an approach identical to the primary analysis but on the dataset with imputed values. The 20 repeats will each be modeled independently, then combined using SAS Proc MI analyze and Rubin's approach (Rubin 1976).

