LS means, standard errors, and the LS mean differences (each treatment versus placebo and the pooled active groups versus placebo) will be reported. All estimates will be generated from a single model, i.e., the pooled estimates will be created via model contrasts. The primary comparison of interest is the difference in the high dose group versus placebo at Visit 5.

Examples of SAS code are provided in Appendix 4.

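### Does the planned 95% CI of ±2.7 / ±3.2 misstate the precision of the primary contrast, higher dose versus placebo?

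*Protocol*

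**What the plan says.** Protocol 9.2, repeated in the synopsis, plans 20 patients in each of three arms and takes the ESS-CHAD SD to be 5 to 6. At SD 5, "the study would be powered at 80% to detect a difference of 3.9 between the pooled pitolisant groups and placebo group". It then says that statistical separation is not a strict aim of a proof-of-concept trial, and that the sample size "will yield a 95% confidence interval of ± 2.7 with an SD of 5 and ± 3.2 with an SD of 6". The sentence ends: "this will give sufficient precision to inform future studies". It names neither the comparison nor the type of SD (raw score or change).

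The primary contrast is fixed elsewhere. The synopsis and Protocol 9.4.2.1.1 state: "The primary contrast of interest is the difference in the higher dose group versus placebo at Week 11". The estimand in Protocol 9.1.1 agrees: "from Baseline to Week 11 for higher dose pitolisant compared with placebo". So does SAP 12.4.1.3.3: "The primary comparison of interest is the difference in the high dose group versus placebo at Visit 5". In Protocol 9.1.2 the comparison "for the combined pitolisant dose groups compared with placebo" comes third among those on the primary endpoint, after the higher and the lower dose. On how the contrasts are estimated, Protocol 9.4.2.1.1 says: "All estimates will be generated from a single model, i.e., the pooled estimates will be created via model contrasts".

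SAP 8.2 carries the same paragraph with its numbers blacked out. Its legible text names only the pooled comparison, and adds that separation is even less of an aim for the individual doses. SAP 12.4.1.1 says that the study is not powered for significance.

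**The concern.** Once the protocol sets statistical separation aside, the width of the confidence interval is the main justification left for the sample size. One expects that width to be given for the contrast called primary. The ±2.7 and ±3.2 instead match a comparison in which the active side is twice as large.

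A reader who knows that the primary contrast is higher dose versus placebo, and applies the printed figures to it, would expect a narrower interval than 20 against 20 supports. The stated purpose is to inform later studies, and Protocol 1.3.2 shows that higher-dose efficacy signals did feed a later dosing decision. An optimistic figure for that contrast would therefore fall on the comparison that was used.

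**Working it through.** **Inputs.** Arm sizes of 20, 20 and 20, and SD 5 to 6, from Protocol 9.2. Two-sided tests, from SAP 12.4.1.1. The 5% level is taken from the 95% interval, because the level in SAP 12.0 is blacked out. Protocol 9.2 mentions neither a dropout allowance nor a gain from baseline adjustment, so both are set to zero at first.

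**Formula.** Half-width = 1.96 × SD × √(1/n₁ + 1/n₂).

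**The plan's own figures.** For pooled pitolisant versus placebo, 1/40 + 1/20 = 0.075 and √0.075 = 0.2739.

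- SD 5: SE = 1.369; half-width = 2.68, printed as 2.7.
- SD 6: SE = 1.643; half-width = 3.22, printed as 3.2.

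Both reproduce. With a t quantile they would be 2.74 and 3.29, and the second would print as 3.3, so the printed pair is a normal approximation. The power statement reproduces on the same contrast: at SD 5 with 40 against 20, a difference of 3.9 has power 0.800 by the noncentral t (0.813 by the normal approximation).

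**The primary contrast on the same basis.** For 20 against 20, 1/20 + 1/20 = 0.100 and √0.100 = 0.3162.

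| | 40 vs 20 | 20 vs 20 | gap |
|---|---|---|---|
| SD 5, normal | ±2.68 | ±3.10 | 0.42 |
| SD 6, normal | ±3.22 | ±3.72 | 0.50 |
| SD 5, t with 57 df | ±2.74 | ±3.17 | 0.42 |
| SD 6, t with 57 df | ±3.29 | ±3.80 | 0.51 |

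The 57 df are 60 − 3, because all contrasts come from one three-arm model. The ratio is √(0.100/0.075) = 1.155 on either basis.

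**How firm is the 40 vs 20 reading?** The planned MMRM adjusts for baseline. If the SD of 5 to 6 is that of a raw score, adjustment multiplies the variance by 1 − ρ², where ρ is the correlation between baseline and Week 11. The documents give no ρ, so a range is assumed. For 20 against 20 (normal approximation):

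| assumed ρ | SD 5 | SD 6 |
|---|---|---|
| 0 | ±3.10 | ±3.72 |
| 0.3 | ±2.96 | ±3.55 |
| 0.5 | ±2.68 | ±3.22 |
| 0.7 | ±2.21 | ±2.66 |

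At ρ = 0.5 the factor is 0.75, and 0.75 × 0.100 = 0.075, so the printed pair would be exactly right for the primary contrast. Against that reading, the same gain would bring the pooled detectable difference at SD 5 down to 3.90 × √0.75 = 3.38, not the stated 3.9. Pooled versus placebo without adjustment is therefore the simpler reading. It is not proven, because the paragraph already mixes a t-based power figure with normal-based half-widths.

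**The case for a change.** The best case for a change is that precision carries the justification, the primary contrast is declared unambiguously in both documents, and nowhere is its planned half-width printed. The pooled comparison can be inferred from the power sentence, but a sentence about statistical separation stands between the two, and the interval is attributed only to the sample size. Relaxing the aim of separation for individual doses, as SAP 8.2 does, supplies no precision for them. Naming the contrast and adding one figure would cost two edited paragraphs.

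The facts in that case stand: the contrast and the SD type are unlabelled, and the higher-dose figure is absent. Two things do not follow. First, no printed number is wrong, and sizing a proof-of-concept trial on the pooled effect is legitimate when pooled versus placebo is itself a listed comparison on the primary endpoint. Secondly, a reviewer cannot dictate the missing figure. It is ±3.1 and ±3.7 only without a baseline gain, and the range over plausible correlations includes the printed values. The link to the later dosing decision is also weak, because Protocol 1.3.2 cites observed efficacy signals, population PK simulations and safety data, and no planned interval width.

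**Conclusion.** The concern does not call for a change. The printed ±2.7 and ±3.2 are correct for pooled pitolisant versus placebo, the one comparison that the paragraph names. Read as the precision of higher dose versus placebo, they would be too narrow by 0.42 points (SD 5) or 0.50 points (SD 6), or 15% in relative terms. This assumes the full 20 per arm, no dropout and no baseline gain. With a raw-score SD and a correlation of about 0.5 the shortfall disappears.

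The documents set no width that the trial must reach, so nothing shows that ±3.1 would be inadequate where ±2.7 is adequate. Anyone planning a later study will use the standard error of the fitted higher-dose contrast and not this planning figure. Protocol 1.3.2 describes the double-blind phase as completed, so no decision on numbers remains open. A statistician who wants the planned width for 20 against 20 can get it from the stated SD in one line. What remains is a gap in labelling: filling it would make the paragraph clearer but would alter no enrolment, analysis, result or conclusion.
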